3.1 Objectives

To evaluate the immunogenicity and safety of the recombinant novel coronavirus vaccine (adenovirus type 5 vector) in healthy adults aged 18 years and above.

3.2 Trial design

This study is a randomized, double-blind, placebo-controlled phase II clinical trial.

3.3 Sample size

This phase 2 trial is launched before we obtaining the immunogenicity data from the phase 1 trial. Therefore, the sample size of is not calculated, but determined based on expert experiences and the minimum sample size requirement in the technical guidelines for vaccine clinical trials issued by National Medical Products Administration, China. The final sample size is 250 in the middle dose group, 125 in

the low dose group and 125 in the placebo group, with a total sample size of 500.

The antibodies of all participants are measured by ELISA at day 0, day 14, day 28 and month 6, and the antibodies of participants are measured by live SARS-CoV-2 or pseudovirus neutralization test at day 0, day 28, and month 6.

3.4 Randomization and blinding

3.4.1 Randomization and grouping

In this study, randomization and blindness will be achieved by blinding the investigational vaccines. Qualified test vaccines and placebos will be provided by the sponsor, and then be blinded by a third party. SAS software is used to generate random codes by block randomization, and the test vaccine and placebo will be randomly assigned to serial numbers (the vaccine for each participant has a unique serial number). Participants will be randomly divided into the middle dose group, low dose group, and placebo group at a ratio of 2:1:1.

The investigator assigned the random numbers in order of the eligible participants arrived at the place where study number assigned, and filled the screening number and initials into the corresponding column of the random number assignment table, the corresponding number is the study number. In order to control the selection bias of age and gender, the age and gender distribution among the groups should be balanced as much as possible.

3.4.2 Blind code preservation

The statistical blinding staff will write the blinding procedure of randomization to make blind code. The blind code includes the first-level blind code and the second-level blind code. The first-level blind code is the group code, and each vaccine number, or study number, corresponding to each group (low dose group, middle dose group, placebo group) is represented by a different letter. The second-level blind code will reveal the final blind code, namely the name of the group (low dose group, middle dose group, placebo group). Two blind code copies will be put into envelopes, sealed and kept by

the investigator and the sponsor respectively. Emergency letters are also made independently by the blinding staff, sealed and handed over to the investigator for storage. Blinding staff shall not participate in the clinical trial work, and at the same time, they shall not disclose the contents of blinding to any person participating in the clinical trial work.

3.4.3 Replacement vaccines

In order to prevent accidents such as damage to the blinded vaccine during the trial, additional replacement vaccines have been prepared for each group (8 boxes for the middle dose group, 4 boxes for the low dose group, and 4 boxes for the placebo group). The number of replacement vaccines is represented by four letters, each letter corresponding to 4 boxes of replacement vaccines. During the trial, when the replacement vaccine is needed, the vaccination staff will open the replacement vaccine letter corresponding to the participant's study number, and the participant will be vaccinated according to the replacement vaccine number recorded in the letter.

3.4.4 Unblinding

Unblinding time will be jointly decided by the sponsor and the investigator based on the progress of the study. The blinding documents will be jointly signed by the principal investigator, the sponsor and the statisticians.

After the last participant completed V2 (day 28), materials will be sorted out, the blind review being completed, and an independent third party conducted unblinding for the first analysis. Using the two-level unblinding method. The first unblinding is done after the blind review being completed and the data of the first analysis being locked, and then opened the first-level blind code, the group code corresponding to each participant is revealed, and the group is determined. The second unblinding will be carried out after the final statistical analysis report is finalized, and then open the second-level blind code to reveal the group corresponding to each group code.

3.4.5 Emergency unblinding regulations

If serious complications and adverse events occur during the trial, which affect the

choice of treatment measures, the investigators can break the blindness urgently if they think it is necessary to know the group of the participant. When it is necessary to break the blindness, the person in charge of the study center will open the emergency letter corresponding to the participant's study number and reveal their grouping information. The randomization letter should be signed by the person in charge of the study center after use and kept properly. After unblinding, the principal study institutions, the sponsor, the ethics committee and the CRA shall be notified in time.

3.4.6 Blind state maintenance

During the implementation of this clinical trial, the double-blind state should be maintained, that is, neither the investigator nor the participants know whether the participant receive the vaccine or placebo.

The first analysis will be completed by an independent statistician, the statistician unblinded independently for statistical analysis, and submitted the first analysis report to the sponsor and the investigator. The grouping information of participants shall not be disclosed in the first analysis report. The study site will remain double-blind, and the blind code shall not be revealed during the entire clinical trial.

3.5 Inclusion and exclusion criteria

Inclusion criteria

- Aged 18 years and over.
- Able to understand the content of informed consent and willing to sign the informed consent.
- Able and willing to comply with the requirements of the clinical trial protocol and able to complete a 6-month study follow-up.
- Negative in HIV diagnostic blood test.
- Axillary temperature $\leq 37.0^{\circ}\text{C}$.
- Negative serum IgM and IgG to the SARS-CoV-2.
- A body mass index (BMI) are between 18.5 and 30.0.

- General good health as established by medical history and physical examination.

Exclusion criteria

- Family history of seizure, epilepsy, brain or mental disease
- Participant that has an allergic history to any ingredient of vaccines
- Woman who is pregnant, breast-feeding or positive in pregnancy test on day of enrollment, or is planning to be pregnant during the next 6 months
- Any acute fever disease or infections
- Have a medical history of SARS infection
- Have serious cardiovascular diseases, such as arrhythmia, conduction block, myocardial infarction, severe hypertension and not well-controlled
- Major chronic illness, such as asthma, diabetes, or thyroid disease, and not well-controlled
- Hereditary angioneurotic edema or acquired angioneurotic edema
- Urticaria in last one year
- Asplenia or functional asplenia
- Platelet disorder or other bleeding disorder may cause injection contraindication
- Faint at the sight of blood or needles.
- Prior administration of immunodepressant or corticosteroids, antianaphylaxis treatment, cytotoxic treatment in last 6 months
- Prior administration of blood products in last 4 months
- Prior administration of other research medicines in last 1 month
- Prior administration of attenuated vaccine in last 1 month
- Prior administration of subunit vaccine or inactivated vaccine in last 14 days
- Being treated for tuberculosis
- Any condition that in the opinion of the investigators may interfere with the evaluation of study objectives

4 Investigational vaccine and inoculation Method

4.1 Investigational vaccine

The recombinant novel coronavirus vaccine (adenovirus type 5 vector) and placebo are developed by the Beijing Institute of Biotechnology and CanSino Biologics Inc.

The recombinant novel coronavirus vaccine (adenovirus type 5 vector) is a liquid formulation, using replication-defective human adenovirus type 5 as a vector, and express the specific S protein of the SARS-CoV-2. The quality of the test vaccine is in line with the “recombinant novel coronavirus vaccine (adenovirus type 5 vector) manufacturing and verification regulations (draft)” formulated by the sponsor. The recombinant novel coronavirus vaccine (adenovirus type 5 vector) has got the certification from National Institutes for Food and Drug Control.

The placebos contain no replication-defective human type 5 adenovirus that expressed the S protein of SARS-CoV-2, and the other ingredients are consistent with the test vaccine and are approved by National Institutes for Food and Drug Control.

In addition to providing adequate quantities of investigational vaccines, the sponsor shall provide replacement vaccines at 5 percent of the number of vaccines required for each group. If the investigational vaccine is damaged or otherwise unavailable, it should be discarded. Although in such cases (with the exception of cold-chain incidents) the sponsor need not be notified immediately, the investigator should keep a detailed record of the damage to the investigational vaccine.

4.2 Immunization procedure and immunization pathway

All investigational vaccines will be immunized by single dose, and the immunization pathway is intramuscular injection of the lateral deltoid muscle of the upper arm.

Middle-dose group: 2 vials of investigational vaccine will be extracted with a syringe, the total volume is 1ml, and the total dosage is 1×10^{11} vp.

Low-dose group: 1 vial of investigational vaccine and 1 vial of placebo will be extracted with a syringe, the total volume is 1ml, and the total dosage is 5×10^{10} vp.

Placebo control group: 2 vials of placebos will be extracted with a syringe, the total

volume is 1ml, and the total dosage is 0vp.

Before injection, 75% alcohol is used for disinfection at the injection site and then intramuscular vaccination will be administrated. Shaking the vaccine before use. No intravascular, intradermal or subcutaneous injection is allowed with the investigational vaccine. Participants should be carefully observed for at least 30 minutes after vaccination and appropriate emergency medical treatment should be in place to prevent possible allergic reactions after vaccination.

5 Study endpoints

5.1 Primary endpoint

5.1.1 Safety endpoint

- Occurrence of adverse reactions (AR) within 14 days after vaccination.

5.1.2 Immunogenicity endpoint

- Geometric mean titer (GMT) of antigen-specific antibody at day 28 after vaccination measured by ELISA.
- Geometric mean titer (GMT) of specific neutralizing antibody against SARS-CoV-2 at day 28 after immunization measured by live SARS-CoV-2 and pseudovirus neutralization test.

5.2 Secondary endpoint

5.2.1 Safety endpoint

- Occurrence of adverse events (AE) within 14 days after vaccination.
- Occurrence of adverse events (AE) within 28 days after vaccination.
- Occurrence of serious adverse events (SAE) within 28 days after vaccination.
- Occurrence of serious adverse events during the whole follow-up period (6 months).

5.2.2 Immunogenicity endpoint

- Geometric mean titer (GMT) of antigen-specific antibody at day 14, and month 6 measured by ELISA.

- Geometric mean titer (GMT) of specific neutralizing antibody against SARS-CoV-2 at month 6 after immunization measured by live SARS-CoV-2 and pseudovirus neutralization test.
- Seroconversion rate of antigen-specific antibody at day 14, day 28, and month 6 measured by ELISA.
- Geometric mean fold increase (GMI) of antigen-specific antibody at day 14, day 28, and month 6 measured by ELISA.
- Seroconversion rate of specific neutralizing antibody against SARS-CoV-2 at day 28, and month 6 measured by live SARS-CoV-2 and pseudovirus neutralization test.
- Geometric mean fold increase (GMI) of specific neutralizing antibody against SARS-CoV-2 at day 28, and month 6 measured by live SARS-CoV-2 and pseudovirus neutralization test.
- Geometric mean titer (GMT) of neutralizing antibody against Ad5 at day 28, and month 6.
- Geometric mean fold increase (GMI) of neutralizing antibody against Ad5 at day 28, and month 6
- The positive rate and level of IFN- γ stimulated by S protein overlapping peptide library at day 28 measured by ELISpot.

For uncertain values: when calculating GMT, GMI and seroconversion of antibodies, if the antibody level is below the initial detection limit, half of the initial value will be used; if the antibody level is greater than the detection limit, the maximum dilution will be used.

5.3 Exploratory endpoint

- The correlation between antigen-specific antibody measured by ELISA and neutralizing antibody against SARS-CoV-2.
- The persistence of the antigen-specific antibody measured by ELISA at month 6.

6 Statistical analysis population

6.1 Data set for safety evaluation

All participants who received vaccination after randomization should be included in the safety evaluation. Data of the participants who violate the protocol should not be excluded.

6.2 Data set for immunogenicity evaluation

Full analysis set (FAS): FAS is based on ITT (intention to treat analysis) principle to determine the participants. All of the participants that meet the inclusion/exclusion criteria, receiving randomization and vaccination, and have at least one blood testing result after vaccination, should be included in the FAS for immunogenicity.

Per-protocol set (PPS): It is a subset of FAS. The participants in this data set will be more compliant to the protocol, with no significant deviation or violation of protocol, all meet the selection/exclusion criteria and completed vaccination within the vaccination time window according to the requirements of the protocol, and the participants who being collected blood at day 0, day14, day 28, and month 6 will be included in the PPS. This method of analysis does not include participants who violate the protocol, and confirmed COVID-19 cases during the study.

In this trial, the FAS is the primary analysis set for immunogenicity evaluation, but the PPS will also be analyzed. Any difference of analysis results between PPS and FAS will be discussed in the report.

7 Data processing specifications

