8.9 Analysis Plan

8.9.1 First analysis

After the last participant completes visit 2 (28 days after immunization), and the study database is entered, reviewed and locked, it can be handed over to the independent statistical party for the first analysis. The first statistical analysis report must be reviewed by the DSMB to determine that the report is carried out in strict accordance with the first statistical analysis plan before it can be submitted to the investigators and sponsors.

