8.9.2 Final analysis

After the last participant completes visit 3 (month 6), collect the data of serious adverse events, humoral immunity and cellular immunity from visit 2 (day 28) to visit 3 (month 6), and carry out final statistical analysis and summary.

9 Statistical tables

See CM20200407 a phase II clinical trial of the recombinant novel coronavirus vaccine_tableshell_V1.0_20200518.

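### The single per-protocol set requires a month-6 blood sample, so it is empty or very small at the day-28 first analysis and later selects day-28 titres on events after day 28

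*SAP*

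**What the plan says.** SAP section 6.2 defines one PPS as a subset of the FAS. On blood samples it says that "the participants who being collected blood at day 0, day14, day 28, and month 6 will be included in the PPS". The four visits are joined by a plain conjunction. There is no qualifier such as 'as applicable' and no version of the set for a single visit. The section then adds an exclusion with no time limit: "This method of analysis does not include participants who violate the protocol, and confirmed COVID-19 cases during the study".

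The roles of the two sets are stated as "In this trial, the FAS is the primary analysis set for immunogenicity evaluation, but the PPS will also be analyzed", and section 6.2 commits the report to discussing any difference between them. For the FAS a participant must, besides meeting the entry criteria and being randomized and vaccinated, "have at least one blood testing result after vaccination, should be included in the FAS for immunogenicity".

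The primary immunogenicity endpoints in section 5.1.2 are both at day 28: "Geometric mean titer (GMT) of antigen-specific antibody at day 28 after vaccination measured by ELISA" and "Geometric mean titer (GMT) of specific neutralizing antibody against SARS-CoV-2 at day 28 after immunization measured by live SARS-CoV-2 and pseudovirus neutralization test".

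Section 8.9.1 times the first analysis: "After the last participant completes visit 2 (28 days after immunization), and the study database is entered, reviewed and locked". Section 8.9.2 times the final analysis: "After the last participant completes visit 3 (month 6").

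**The concern.** A per-protocol set for a day-28 endpoint should depend on what happened up to day 28. This one depends on a blood sample and a disease status that are known only months later. There are two consequences.

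- **At the first analysis** the primary endpoints are first reported, but the month-6 condition can be met by nobody, or only by the earliest enrolled. The team would have to omit the PPS analysis or settle another population. If that is not done at the blind review, it happens after the lock, when under sections 3.4.4 and 3.4.6 the independent statistician opens the group codes.
- **At the final analysis** a participant with a valid day-28 titre leaves the day-28 PPS comparison for missing the month-6 visit or for having COVID-19 after day 28. Both come after the measurement. Infection may plausibly depend on arm and on antibody level, so the selection may differ between arms. A difference between FAS and PPS then mixes compliance up to day 28 with later retention and infection.

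**Working it through.** The SAP states no figure on this point that could be reproduced, and section 3.3 says that the sample size was not calculated. The check is therefore one of timing and counts.

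**Inputs from the SAP.** Total 250 + 125 + 125 = 500 (section 3.3); PPS bleeds at day 0, day 14, day 28 and month 6 (section 6.2); first analysis after the last day-28 visit (section 8.9.1).

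**Assumptions, because the SAP gives no value.** Accrual span S in days, with uniform accrual; month 6 taken as 168, 180 or 183 days; attendance per bleed of 95% or 98%, independent between bleeds.

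**Step 1: can anyone qualify at the first analysis?** When the last participant reaches day 28, the first participant has been followed for S + 28 days. A month-6 sample can exist only if S + 28 exceeds month 6, so S must exceed month 6 minus 28.

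| Month 6 taken as | Accrual needed before anyone qualifies |
|---|---|
| 168 days | 168 − 28 = 140 days |
| 180 days | 180 − 28 = 152 days |
| 183 days | 183 − 28 = 155 days |

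For any shorter span the PPS holds 0 of 500. For longer spans the share that has reached month 6 is (S + 28 − month 6) / S.

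| Accrual span | Month 6 = 168 | Month 6 = 180 | Month 6 = 183 |
|---|---|---|---|
| 160 days | 20/160 = 12.5% | 8/160 = 5.0% | 5/160 = 3.1% |
| 180 days | 40/180 = 22.2% | 28/180 = 15.6% | 25/180 = 13.9% |

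These shares are upper limits, because they ignore the other PPS conditions and any missed visits.

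**Step 2: how many does the month-6 bleed remove at the final analysis?** Compare the requirement for three bleeds (day 0, 14, 28) with that for four.

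- At 95%: 0.95³ − 0.95⁴ = 0.857 − 0.815 = 0.043, and 0.043 × 500 ≈ 21.
- At 98%: 0.98³ − 0.98⁴ = 0.941 − 0.922 = 0.019, and 0.019 × 500 ≈ 9.

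**Step 3: how far could the day-28 GMT move?** Let a share d miss month 6, and let their day-28 GMT be g times that of those retained. The retained GMT exceeds the GMT of all participants by the factor g^(−d). Both d and g are assumed.

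| Share lost, d | g = 0.7 | g = 0.5 |
|---|---|---|
| 5% | 1.018 | 1.035 |
| 10% | 1.036 | 1.072 |
| 20% | 1.074 | 1.149 |

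The shift is about 2 to 4% at 5% loss, 4 to 7% at 10% and 7 to 15% at 20%. The COVID-19 exclusion is not quantified, because the SAP gives no expected number of cases.

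**The case against.** **The primary result is not at risk.** A reader might infer that the day-28 primary analysis itself fails. It does not. The FAS is primary and needs only one post-vaccination result, so the day-28 GMTs can be produced at the first analysis. This stands, and it limits the weight of the point.

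**An empty set is not certain.** A reader might take 0 of 500 as fact. It rests on an accrual period that the SAP does not give. This stands too, but the alternative is a small group of early enrollees, which is no usable per-protocol analysis either.

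**No PPS analysis is expressly scheduled at the first analysis.** Section 8.9.1 names no population, and it mentions a statistical analysis plan for the first analysis that could be another document. That the PPS is due then is an inference. It is a reasonable one, since section 6.2 limits the PPS to neither analysis and the primary endpoints belong to the first. Nothing in this SAP supplies a day-28 set.

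**The list of bleeds could be meant visit by visit.** Possibly, but the wording does not say so.

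**The loss could be overstated.** Comparing all four bleeds with day 0 and day 28 alone gives about 44 participants at 95% (0.95² − 0.95⁴ = 0.088) and 19 at 98% (0.98² − 0.98⁴ = 0.038). Those figures include the day-14 bleed, which precedes day 28 and is no later event. Requiring it is a conventional strict choice, and day 14 is an ELISA visit. Only about 21 and 9 belong to this point. If the same people tend to miss several visits, the numbers are smaller still.

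**A FAS/PPS difference would not be meaningless.** Under the assumed scenarios at 5 or 10% loss the shift is modest, and the result could be described as a completer analysis. What is lost is its reading as a per-protocol result for day 28.

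**Conclusion.** The PPS definition is wrong as written and should be fixed. It does not undermine the primary immunogenicity result.

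- At the day-28 first analysis no participant can qualify if accrual takes no more than about 140 to 155 days. With 180 days, at most about 14 to 22% could.
- At the final analysis the PPS day-28 GMT is selected on month-6 attendance and on COVID-19 after day 28. The month-6 rule alone costs about 21 of 500 at 95% attendance per bleed, or about 9 at 98%, if attendance is independent between bleeds.
- What fails is the supportive PPS analysis and the FAS/PPS comparison that section 6.2 promises.

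The structural defect follows from the SAP's wording alone. Its size rests on the assumed accrual span, length of month 6 and attendance.

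**What to change.** Replace the single PPS in section 6.2 with three visit-specific sets, for day 14, day 28 and month 6. Each should use only vaccination compliance, protocol deviations and samples up to its own visit, and should require valid samples at day 0 and at that visit. State in section 8.9 which sets are used at the first and at the final analysis.

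For COVID-19, remove a participant's titres from the visit at which infection could have affected the sample, and keep earlier titres. Counting only from the date of confirmation is not enough, because a sample drawn after infection but before confirmation would stay in. The look-back from confirmation should be written down before unblinding.

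Whether the day-28 set should also require the day-14 bleed is a separate choice for the sponsor. The SAP should state it either way.

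The cost is SAP wording and one population flag per visit. No further data are needed and participants are not affected.
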